5.4. Pediatric RSV Electronic Severity and Outcome Rating System (PRESORS)

5.4.1. Definition

Currently, no single outcome assessment tool is widely accepted to assess the severity of RSV in infants and children. Although various clinical scores have been developed for the evaluation of the severity of acute respiratory infections and/or bronchiolitis in infants and children, none have been sufficiently validated for the longitudinal monitoring of the severity of RSV infection. Considering that there are no widely accepted or fully validated clinical endpoints for use in studies of RSV treatment, the PRESORS, an electronic clinician and parent/caregiver RSV infection severity rating assessment, will be further developed and evaluated for validity and reliability in a phase 0 trials, 64041575RSV0001.

The PRESORS data may also be analyzed for specific psychometric properties outside the scope of this protocol (possibly in conjunction with data from study 64041575RSV0001). In that case results will also be reported separately.

This study includes the same version of the PRESORS as in this validation study. The scoring system that will be used during this validation is available in attachment 4.

The PRESORS scores are defined as in table below. These will be calculated at each scheduled time point a questionnaire was filled in. A change from baseline will also be calculated.

Domain	Items	Scoring
Severity of signs and symptoms during the past 12 hours as assessed by the Clinician	Attachment 4: Items 1-5 (Clinician)	Sum of the individual item scores. See appendix for item score.
Severity of signs and symptoms now as assessed by the Clinician	Attachment 4: Items 6-14 (Clinician)	Sum of the individual item score. See appendix for item score.
Study drug administration as assessed by the Clinician	Clinician's Items: Study drug administration	Number of reports, ranging from 0 (no reports) to 6.
Severity of signs and symptoms as assessed by the Caregiver	Attachment 4: Items 1-12 (Caregiver)	Sum of the individual item score. See appendix for item score.
Breaths/minute	Caregiver: Breaths/15s	4 times the Breaths per 15 seconds
Improvement during the past 12 hours as assessed by the Clinician	Attachment 4: Items 1-5 (Clinician)	Number of signs and symptoms that have decreased by at least 2 points during the past 12 hours as assessed by the Clinician per time point.
Improvement now as assessed by the Clinician	Attachment 4: Items 6-14 (Clinician)	Number of signs and symptoms that have decreased by at least 2 points now as assessed by the Clinician per time point.

Improvement as assessed by the Caregiver	Attachment 4: Items 1-12 (Caregiver)	Number of signs and symptoms that have decreased by at least 2 points as assessed by the Caregiver per time point.
------------------------------------------	------------------------------------------------------------	--------------------------------------------------------------------------------------------------------------------

5.4.2. Analysis Methods

Frequency tabulations of each of the individual items at baseline, day 7, 14 and 28.

Severity and Improvement of Signs and Symptoms of the RSV infection

Actual values and changes from baseline will be summarized by treatment group at each scheduled time point for the PRESORS scores (severity), child's temperature, breaths per minute, time spent with the child and hours missed from usual activities.

Mean \pm SE graphs over time for the actual values and changes from reference will be presented.

Analyses of the PRESORS scores may be performed to further investigate validity of this instrument. These will be described outside this SAP and, if performed, will be reported outside the CSR.

Duration of Signs and Symptoms of the RSV infection

See secondary endpoint: Time to readiness for discharge.

Relationship between viral load and duration of signs and symptoms of RSV symptoms as assessed by the PRESORS questionnaire completed by the clinician

Kaplan-Meier analysis by quartiles of viral load AUC_{0-7 days} for the duration of signs and symptoms of RSV symptoms

A summary table including number of subjects included in the analysis, number of subjects censored, 25th and 75th percentiles and median with 95% confidence intervals based on log-log transformation method, will be presented by quartiles of viral load AUC_{0-7 days} parameter.

The relationship between the clinician eCOA and parent(s)/caregiver(s) eCOA responses

The relationship between the severity of signs and symptoms as assessed by the clinician and the parent(s)/caregiver(s) will be assessed using spearman rank correlation between the clinician's score (both during the past 12 hours and now) and the parent(s)/caregiver(s) score. This correlation will be evaluated at baseline and on all scheduled assessments where both the clinician eCOA and caregiver eCOA have been performed. Other methods may be considered as appropriate.

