- None of these were reported [*cannot be checked if other options selected*]

17.2 During study drug administration, were any of the following reported? (note all that apply)

- Spit out or coughed out medicine
- Gagged or wretched
- Vomited (within 2 minutes of swallowing medicine)
- None of these were reported [*cannot be checked if other options selected*]

At Day 7 and during the end-of-study visits only, clinicians will be asked the following clinician's global rating of change (CGRC) question:

18. With respect to the child's RSV infection, how would you describe the child's health now compared to the baseline assessment?

-5	-4	-3	-2	-1	0	1	2	3	4	5
Very much worse					Unchanged					Very much better

Screen shown after final question for the assessment has been entered.

Thank you for completing this assessment.

Pediatric RSV Electronic Severity & Outcome Rating System (PRESORS) v6**Caregiver diary**

[completed at screening and throughout the study until the end of follow-up]

Enter your user ID

Enter your passcode

Caregiver demographic questions 1-7 to be completed the first time the caregiver completes the diary

1. How are you related to the child in this study? (select one)

- Parent, step parent, or foster parent
- Grandparent
- Other family member
- Nanny or day care provider
- Neighbor or friend of the parent
- Other

2. Do you live with the child in this study? Yes No

3. There are 168 hours in a week. Counting time even when the child is asleep, how many hours do you usually take care of the child each week? hours/week

4. What year were you born? year born

5. Are you male or female? Male Female

6. How many years of education have you completed? years

7. What best describes your employment status? (select one)

- Full-time paid employment
- Full-time homemaker
- Part-time paid employment
- Retired
- Disabled, unable to work due to health problems
- Unemployed, looking for work
- Other

Caregiver diary entry to be completed by caregiver at each assessment except as noted

PRESORS Caregiver diary

It is now time to complete your caregiver diary.

For each question, please mark the answer or answers that best describe how the child has been *[during the appropriate recall period for the assessment, see table below]*

Assessment timing	Recall language
Screening and baseline (If ≥ 12 hours post screening)	“over the last 12 hours”
Twice daily post baseline through Day 14	
Upon waking in the morning	“since bedtime last night”

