Evening at the child’s usual bedtime	“since the child woke up this morning”
For studies with more than 7 days follow-up post baseline, once daily in the evening assessments from Day 15 through end of follow-up	“since this time yesterday”
At the Day 28 post-treatment follow-up visit	“over the last 24 hours”

1. Overall, how has the child’s health been *[recall period]*?

- Excellent
- Good
- Fair
- Poor

2. If the child was awake at all *[recall period]*, how active was the child?

- As active as usual
- A little less active than usual
- A lot less active than usual
- Floppy or limp, not responding to you as usual

For 12-hour recall phase use Question 3a

3a. How much did the child sleep *[recall period]*? (select one)

- A lot less than usual
- A little less than usual
- About as much as usual
- A little more than usual
- A lot more than usual

For 24-hour recall phase use Questions 3b and 3c

- 3b. How much did the child sleep during the day during the past 24 hours? (select one)
- A lot less than usual
 - A little less than usual
 - About as much as usual
 - A little more than usual
 - A lot more than usual
- 3c. How much did the child sleep during the night during the past 24 hours? (select one)
- A lot less than usual
 - A little less than usual
 - About as much as usual
 - A little more than usual
 - A lot more than usual
4. Was the child crying more than usual [*recall period*]? (select one)
- Normal, no more crying than usual
 - Cried more than usual but calmed if held or soothed
 - Cried a lot, difficult to calm even if held or soothed
 - Cried a lot, would not stop crying even if held or soothed
5. Do you hear wheezing or whistling sounds in the child's chest when the child breathes? (select one)
- No
 - Yes, but only at the end of when the child breathes out
 - Yes, throughout breathing out
 - Yes, throughout breathing in and out

6. There are signs you can see when a child has breathing problems.
- 6.1. Did the child show these signs of breathing problems [*recall period*]? (note all that apply)
- Breathing through mouth because of difficulties breathing through stuffy or runny nose
 - Gasping for air and/or long pauses between breaths
 - Breathing faster than usual
 - None of these [*option cannot be checked if any of the other options are selected*]
- 6.2. Did the child show any of these signs of breathing problems [*recall period*]? (note all that apply)
- Ribs more visible than usual when child breathes in

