10.1. Did the child only vomit when coughing [*recall period*]? (select one)

- No
- Yes

11. Did the child eat, drink or nurse as usual [*recall period*]? (select one)

- Yes, ate, drank or nursed as usual
- No, a little less than usual
- No, a lot less than usual
- No, did not eat, drink or nurse at all

12. Was the child receiving liquids other than medicine through tubes in the nose, mouth or stomach [*recall period*]? (select one)

- Yes
- No

13. Did the child urinate as usual (number of wet diapers or trips to the toilet) [*recall period*]? (select one)

- Yes, as usual
- No, a little less than usual
- No, a lot less than usual
- No, did not wet a diaper or use the toilet

14. Did the child show any of these signs [*recall period*]? (note all that apply)

- Dry skin or lips
- Soft spot on top of the head sunk in
- Sunken eyes
- Dark yellow urine
- Little or no urine
- None of these [*cannot be checked if other options are selected*]

15. Did the child's heart seem to be beating faster than usual?

- Yes
- No

Questions 16-17 are to be completed on the day of hospital discharge and during the morning assessment only through follow-up Day 14

16. Please take and record the child's temperature now

Temperature: ° Fahrenheit (*or Celsius as used locally*)

17. [15 second countdown timer]. Please count how many times the child breathes. Press the button to start the timer. When you hear the first tone, begin counting the child's breaths. **Each time the child breathes in and out counts as 1 breath.** When you hear the second tone, stop counting and record how many breaths you counted.

Start Timer [note: 5 second delay after activating the timer before tone indicating begin timing]

Do you need to count again?

- Yes [back to Start Timer]
 No [go to Enter Count]

How many breaths did you count? [] breaths

At every assessment

18. How many hours did you spend with the child [recall period]?
[] hours
19. How many hours were you unable to do things you usually do such as go to work, household chores, or care for other family members because the child had RSV [recall period]?
I missed [] hours from my usual activities because of the child's RSV

For clinical trials only during AM assessment on Day 7 only

20. In general, how did the child react when he/she was given the medicine? (note all that apply)
- Child took medicine easily [cannot be checked if other options selected]
 - Disgusted expressions after tasting medicine
 - Cried after tasting medicine

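### Caregiver hours items are summarised as raw hours across 12 h and 24 h recall periods, so within-arm trends and the Day 28 change from baseline partly reflect the length of the recall

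*SAP*

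**What the plan says.** The caregiver diary in Protocol Attachment 5 has two items answered in hours at every assessment. Item 18 asks for time spent with the child. Item 19 begins "How many hours were you unable to do things you usually do such as go to work, household chores, or care for other family members". Both refer to the recall period in force, which the diary's recall table sets as follows:

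- Screening and baseline: "over the last 12 hours".
- "Twice daily post baseline through Day 14": the morning entry runs from the previous bedtime, and the evening entry covers the time "since the child woke up this morning".
- "once daily in the evening assessments from Day 15 through end of follow-up": the entry runs from the same time on the previous day.
- Day 28 visit: the preceding 24 hours.

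Hours missed is an exploratory endpoint (Protocol 2.1.2); time with the child is not a listed endpoint. SAP 5.4.2 includes both in its group summaries of observed values and change from baseline ("breaths per minute, time spent with the child and hours missed from usual activities") and adds mean and SE graphs over time. SAP 2.6 defines baseline as the last record before first dose, which for the diary is a 12 h entry.

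**The concern.** An hours item is a total, so it grows with the window it covers. The bounded severity scores in the same diary do not grow in this way. The instrument recognises the difference for sleep: one question serves the 12 h phase, and separate day and night questions serve the 24 h phase.

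The SAP has no matching step for the hours items. SAP 5.4.1 rescales a different diary item (breaths counted over 15 seconds, times 4). The SAP 2.1 rule for measurements scheduled more than once daily names only vital signs and SpO2. Followed as written, the summary sets a 24 h total against a 12 h total and labels the difference a change from baseline. A family whose burden has not changed would look worse, and a family that has recovered in part could look unchanged.

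**Working it through.** The documents give no numerical values for these items, so there is no plan figure to reproduce. The burden levels below are assumptions; the recall lengths come from Protocol Attachment 5.

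**1. Constant hourly burden, 12 h baseline against a 24 h entry.** Let f be the share of each hour affected. Reported hours = f × recall length.

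| f (assumed) | Baseline, 12f | Later, 24f | Ratio | Raw change |
|---|---|---|---|---|
| 0.25 | 3 h | 6 h | 2.0 | +3 h |
| 0.5 | 6 h | 12 h | 2.0 | +6 h |
| 1.0 | 12 h | 24 h | 2.0 | +12 h |

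The true change is zero in every row.

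**2. True improvement from f = 0.5 (baseline entry 6 h, equal to 12 h per 24 h).**

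| True fall | 24 h entry | Raw change | Change in hours per 24 h |
|---|---|---|---|
| 25% | 24 × 0.375 = 9 h | 9 − 6 = +3 h | 9 − 12 = −3 h |
| 50% | 24 × 0.25 = 6 h | 6 − 6 = 0 h | 6 − 12 = −6 h |
| 75% | 24 × 0.125 = 3 h | 3 − 6 = −3 h | 3 − 12 = −9 h |

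**3. Uneven burden, evening entry against a 24 h entry.** With d hours lost by day and n by night, the ratio is (d + n)/d.

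- d = 8, n = 0: 8/8 = 1.0
- d = 6, n = 2: 8/6 = 1.33
- d = 4, n = 4: 8/4 = 2.0

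If the SAP 2.1 averaging rule were borrowed for the diary, the mean of the morning and evening entries would be (d + n)/2. The ratio to the 24 h total is then 2.0 whatever the split.

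**4. Who changes recall, and when.** Under the Time and Events Schedules, discharged children move to one evening diary after Day 14, while children still in hospital stay on twice-daily diaries through Day 28. Protocol Attachment 5 starts the once-daily 24 h recall at Day 15. SAP Attachment 4 lists Day 14 under both the part-day and the 24 h recall. In SAP 2.1 the Day 14 analysis window extends to Day 20 and the next analysis visit is Day 28, from Day 21 onward. A 24 h entry could therefore supply the Day 14 value if the entry due that day is missing, and late visits can mix recall lengths.

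**The case against.** The best case for leaving the plan alone is that little depends on these items. Hours missed is exploratory, the diary analyses are descriptive, and the recall wording is the same in every arm. That largely stands. A reader might infer a biased treatment comparison, but arms compared at the same visit share the same window. The exception is an imbalance in who is still in hospital, because discharge status determines diary frequency and arises after randomisation.

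Three other strong readings also go further than the documents.

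- **The values always double.** Doubling from baseline needs an even hourly burden. Item 19 concerns work, chores and care of others, which may fall mostly in waking hours, and the evening entry already covers the waking day. The 12 h baseline may itself fall by day or by night. Where residual burden at Day 28 is near zero, the artefact is also near zero.
- **A visible step from Day 14 to Day 15.** SAP 2.1 has no Day 15 analysis visit. If the diary follows those windows, the contrast shown is Day 14 against Day 28, to which real recovery also contributes.
- **Everyone switches at Day 15.** The once-daily schedule applies after discharge only.

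None of this supplies a common unit. The Day 28 change from baseline still mixes recall lengths for children on the 24 h recall.

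**Conclusion.** The point holds for within-arm trends and for change from baseline, above all at Day 28. The distortion is a factor of 2 if the hourly burden is constant. Against an evening entry it is about 1 to 2 for the splits examined, where night losses do not exceed day losses. Both figures rest on assumed burden patterns, because the documents give none. Starting from a 50% burden that is even over day and night, a true halving would be reported as no change.

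This is an error in how a named exploratory endpoint would be reported, and it should be corrected. It does not touch the primary or secondary analyses, and same-visit contrasts between arms are largely protected.

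**What to change.** In SAP 5.4.1 and 5.4.2:

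1. Express both items as hours per 24 h. On any twice-daily diary day, including inpatient days after Day 14, sum the morning and evening entries, and only when both are present, so that a missed entry is not read as low burden. Otherwise use the 24 h entry. The alternative is to report each answer as a share of its recall window, which requires a stated length for the overnight and waking windows.
2. Keep the pre-dose baseline. A post-dose reference day could already contain a treatment effect. Doubling the 12 h baseline assumes an even day/night burden, and the SAP should say so. With that scaling, constant burden gives a change of 0 and a halving from f = 0.5 gives −6 h per 24 h. If the assumption is not acceptable, present the 12 h and 24 h recall phases separately, with no change from baseline across the switch.
3. Reconcile the start of the 24 h recall between SAP Attachment 4 (Day 14) and Protocol Attachment 5 (Day 15).

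The cost is SAP wording and one derivation, with no new data. Twice-daily diary days with only one entry drop out of the hours per 24 h summary.
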